The results of other studies [de Lateur et al 1991; Lee et al. 2001; Kwon et al. 2015; Schroeder and Hollander 2018] showed that heel elevation did not significantly change the LL in the female subjects evaluated.

None of the studies reported above take into consideration the time factor. In fact, all the studies have evaluated the immediate changes induced by heel raising. Women who complain of lower back pain when wearing high-heeled shoes rarely experience pain as soon as they start wearing them.

The objective of the research arises from these considerations.

The aim of this study (primary outcome) is to investigate whether wearing high-heeled shoes for at least 2 hours modifies the spinopelvic parameters compared to the barefoot condition and as soon as the shoes are worn.

The secondary outcome will be to verify in the sample analyzed whether there are different behaviors between the subgroups of those who have complained in their anamnesis and those who have never complained of lower back pain when using high-heeled shoes for a few hours.

MATERIALS AND METHODS

Location of the study

Spine Center and OSCE (Osteopathic Spine Center Education), [name]

Population

Students of the OSCE osteopathy school

Sample size

Not having found similar studies in the literature, we prefer to start as a pilot study with the recruitment of approximately 30 female subjects. This number represents a good compromise between the possibility of finding a normal distribution and the feasibility of the study.

Recruitment

Recruitment will be carried out by announcing on the bulletin board and presenting the study project in the classroom of the OSCE osteopathy school.

Following the ethical principles of the Declaration of Helsinki, a paper information will be provided where there will be an explanation of the intent and purpose of the study to all subjects before their participation; furthermore, together with the information, a paper consent will be provided on which to obtain consent written informed voluntary consent to participate in the study and consent to the use of data through privacy information.

Inclusion criteria

- female subjects aged between 20 and 40 years
- usual users of shoes with heels at least 7 cm high, with a frequency of at least twice a week and/or more than 3 hours/week as proposed by a previous study (de Oliveira Pezzan et al. 2011);

Exclusion criteria

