- structural or neurological anomalies that may prevent from standing, for approximately 2 hours, with shoes having a heel (difference between the heel and the plateau) of at least 7 cm high;

Methods

A three-dimensional analysis of the posterior surface will be performed with the Formetric 4D® rasterstereographic device (Diers International GmbH, Schlangenbad, Germany). Participants will be asked to complete the informed consent form after reading the information. Furthermore, consent to the processing of data will be requested after reading the Privacy form, confirming their participation in the study.

Participants will be given a questionnaire which investigates:

- Age, weight, height of the participants;
- Any pain in the spine (measured by NPS) usually reported by subjects after using high-heeled shoes;
- Type of profession;
- Frequency with which the subjects wear the heeled shoe (how many hours per week);
- Heel height of the shoe with which they participate in the clinical study;
- Any spinal pain (measured by NPS) after wearing heeled footwear for the study period.

This last data will be filled in at the end of the evaluation.

For the evaluation of the secondary outcome, on the basis of the data from the medical history sheet, the sample will be divided into two groups:

- 1) The first group (group A, ASYMPTOMATIC) includes subjects who during daily life do not report spinal pain after wearing high-heeled shoes;
- 2) The second group (group S, SYMPTOMATIC) is made up of participants who usually complain of more or less intense pain after using the shoe.

Heel type

The subjects will be asked to bring their own pair of shoes with a heel that is at least 8.7 cm, the average height reported by the work of Schroeder and Hollander (2018), where average height means the difference between the height of the heel and the height of the raised part at the forefoot level (plateau). A particular heel width will not be required, because it seems that the height of the heel influences muscle activation, in particular the paravertebral muscles, while the width of the heel has no significant effects on them (Han 2015).

Conversely, amplitude has a greater influence on balance when standing and while walking.

Measurement method

Positioning with respect to the measurement system will be carried out according to the indications provided by the supplier.

To standardize the position the subjects will be prepared for the analysis as follows:

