1. standing, back to the detection system, in a relaxed posture with knees fully extended with bare feet on the floor (neutral position)
2. bare torso with trousers and briefs lowered to mid-buttock;
3. in the case of long hair, it will be required to tie it with suitable means (cap, hair clips, hair ties, etc.) so that the neck is visible up to the hairline;
4. Rings, watches and necklaces will be removed to avoid any interference with the light lines (necklaces in particular increase this probability).

A three-dimensional analysis of the posterior surface is performed with the Formetric 4D® rasterstereographic device (Diers International GmbH, Schlangenbad, Germany) [9-15].

[figure not shown]
The device, already supplied at the Spine Center rehabilitation center in Bologna and made available free of charge for study, is non-invasive and non-dangerous. The analysis of the spine curve with rasterstereography is carried out with a purely optical modality.

The protocol

- 1) first evaluation in neutral position with bare feet (T0)
- 2) second evaluation in neutral position wearing shoes (T1);
- 3) third evaluation like the previous one but at least 2 hours apart, in which it will be required to remain standing still or walk (T2).

Parameters detected

- 1) Flexion of the antero-posterior trunk (trunk inclination – TI) measured as the angle between the vertical and the line that passes through the prominent cervical vertebra (VP) and the line that connects the two dimples (DM);
- 2) pelvic inclination angle (PI), i.e. the angle between the vertical and the tangent to the lumbosacral junction (ILS);
- 3) ITL-ILS lordotic angle, measured between the tangents of the thoracolumbar junction (ITL) and the lumbosacral junction (ILS);
- 4) ICT-ITL kyphotic angle, measured between the tangents of the cervicothoracic junction (ICT) and the thoracolumbar junction (ITL);
- 5) lumbar arrow (FL) (horizontal distance in millimeters of the lumbar spine from the virtual vertical line that passes through the kyphotic apex) ;
- 6) cervical arrow (FC) (horizontal distance in millimeters of the cervical spine from the virtual vertical line that passes through the kyphotic apex).

Statistic analysis

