A descriptive analysis of the population will be performed to determine the mean values and standard deviations (SD) of both the combined group and the subgroups A and S. T-tests for independent data will be used to verify whether there are any significant differences between the two subgroups .

The distribution of the data will be verified using graphical representation. If the distribution is normal ($p <0.05$) for the comparison between T1 vs T2 the t-test for paired data will be used and between the subgroups (T1S vs T1A and T2S vs T2A) t-test for independent data with statistical significance accepted for p values <0.05 . ANOVA will be used to simultaneously compare the pre and post of both groups.

If the data does not have a normal distribution ($p >0.05$) the Wilcoxon test will be used for the comparison between the T1 vs T2 data of the total group and the Mann-Whitney U test for the comparison between subgroups (T1S vs T1A and T2S vs T2A). The Friedman test will be used to simultaneously compare the pre and post of both groups.

Risks

The risks are quite limited given that the shoes worn are those owned by the tested subject, therefore it is assumed that they are used to wearing them, and they are not asked to perform movements at risk of sprains or falls.

Benefits

Being able to identify the spino-pelvic parameters that predispose to spinal symptoms, when wearing high heels, could help prevent the related pathology/symptoms through postural re-education or muscle strengthening exercises.

Costs

The use of the Formetric will be given free of charge and any related expenses (paper, color cartridges, etc.) will be borne by the Spine Center.

References

de Lateur BJ, Giacconi RM, Questad K, Ko M, Lehmann JF. 1991. Footwear and posture: compensatory strategies for heel height. *Am J Phys Med Rehabil* 70:246–254

de Oliveira Pezzan PA, Joa˜o SMA, Ribeiro AP, Manfio EF. 2011. Postural assessment of lumbar lordosis and pelvic alignment angles in adolescent users and nonusers of high-heeled shoes. *J Manip Physiol Ther* 34:614–621

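### With no equal period on the feet without heels, the change at 2 hours mixes heel wear with standing or walking and cannot be attributed to heels alone

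*Combined protocol and SAP*

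**What the plan says.** The aim, at the end of the Introduction, is to establish "whether wearing high-heeled shoes for at least 2 hours modifies the spinopelvic parameters", relative both to being barefoot and to having just put the shoes on. The Introduction presents duration as what earlier studies left out.

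The section headed The protocol lists three readings:

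- T0: neutral position, barefoot.
- T1: neutral position, wearing the shoes.
- T2: a "third evaluation like the previous one but at least 2 hours apart", the interval being spent standing still or walking.

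No barefoot or flat-shoe reading follows the 2 hours, and there is no session or group without heels. The only grouping is by pain history: "on the basis of the data from the medical history sheet, the sample will be divided into two groups" (Methods). Groups A and S both wear heels.

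Under Statistic analysis, the one paired contrast named for the whole sample is T1 against T2: "for the comparison between T1 vs T2 the t-test for paired data will be used", with Wilcoxon as the alternative. The sample is about 30 women, described as a pilot.

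**The concern.** The aim asks what heels do over time. Between T1 and T2, however, two things accumulate together: time in heels, and time spent upright. Fatigue and time of day can both move a posture reading whatever is on the feet. Because every woman has both exposures for the same period, a drift that comes only from being upright would appear in T2-T1 and could be reported as an effect of prolonged heel wear. This falls on the question the study presents as new and on its main whole-group test. The benefit the protocol hopes for, preventing symptoms linked to heels, also depends on the change being due to the heels.

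**Working it through.** **Inputs.** The conditions at T0, T1 and T2 come from The protocol; the T1 versus T2 paired test and the 0.05 level from Statistic analysis; n = 30 from Sample size. Two-sided testing is assumed, since the plan does not state sidedness. The plan gives no effect size, SD or power, so it has no figure to reproduce.

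**Step 1: what the readings can separate.** For one parameter, on an additive scale, let

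- μ = barefoot mean at the start,
- h = immediate effect of putting heels on,
- d = effect of 2 hours on the feet, whatever the footwear,
- c = added effect of those 2 hours being in heels.

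Then T0 = μ, T1 = μ + h, T2 = μ + h + d + c, and

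- T1 - T0 = h
- T2 - T1 = d + c
- T2 - T0 = h + d + c

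There are three means and four unknowns, and d and c appear only as a sum. A rank check of the design matrix agrees: h is estimable, d and c are not. Comparing A with S does not help, because each group's change is its own d + c. The planned ANOVA or Friedman test uses the same readings and has the same limit.

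**Step 2: how much this could matter.** Suppose c = 0 and d = δ × SD of the paired difference. The T1 versus T2 paired t-test then has noncentrality δ√30 on 29 degrees of freedom, with critical value 2.045.

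| δ (assumed) | δ√30 | P(p < 0.05) |
|---|---|---|
| 0 | 0 | 5% |
| 0.2 | 1.10 | 19% |
| 0.3 | 1.64 | 36% |
| 0.4 | 2.19 | 56% |
| 0.5 | 2.74 | 75% |

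This is bias, so a larger sample raises these percentages.

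**Step 3: what a closing barefoot scan would add.** Let T3 be a barefoot reading straight after T2, and r the carry-over of heels into it. Then T3 = μ + d + r, so

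- T3 - T0 = d + r
- (T2 - T3) - (T1 - T0) = (h + c - r) - h = c - r

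The rank check shows that d and c remain inseparable unless r is taken to be 0. If the heel effect persists once the shoes are off, r approaches c and the second contrast approaches zero, however large c is.

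The second contrast is also noisier. If reading errors are independent with equal variance σ² (assumption), the variance of T2-T1 is 2σ² and that of the four-reading contrast is 4σ², an SD ratio of √2 ≈ 1.41. Even with r = 0, values of c equal to 0.3, 0.4 or 0.5 SD of T2-T1 become 0.21, 0.28 or 0.35 SD of the new contrast. These would be detected 20%, 32% or 47% of the time with n = 30.

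**Step 4: what would separate them.** An equal period on the feet without heels, read before and after, gives d directly, and c = (T2 - T1) minus the no-heel change. The rank check then shows both as estimable.

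**The case against.** The study calls itself cross-sectional and a pilot. The two comparators named in its aim, barefoot and shoes just put on, are exactly T0 and T1, and women normally wear heels while upright. On that view, 2 hours upright in heels is the exposure of interest. This is a fair reading, and it supports limiting the conclusion rather than redesigning the study. It does not support the wording of the aim, which credits the change to the shoes. Pilot status can excuse the lack of a power calculation, but not a contrast that cannot answer the question as put.

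A second objection is that the percentages do not show that drift exists. That stands. They are the rejection rates of a paired t-test with 30 women at assumed shifts, and say only what would follow if drift of that size were present. Repositioning should not be counted as a source of bias either: it occurs at every scan, positioning is standardised, and without a systematic shift it adds only noise.

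A reader might infer that the gap is simply the missing barefoot reading at the end, and that adding one would settle attribution. The documents do not support this. The Introduction's suggested mechanism is greater paraspinal muscle activation, and nothing in the plan says that its consequences vanish when the shoes come off. Making attribution depend on c - r could therefore hide the very effect the study seeks.

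**Conclusion.** The concern holds as a limit on interpretation. With T0, T1 and T2 alone, T2-T1 and T2-T0 cannot be attributed to heel wear, because no woman spends a comparable period on her feet without heels. This follows from the design and needs no numerical assumption beyond the additive description used above.

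The size is conditional: 36%, 56% or 75% significant results with no effect of heel duration if drift is 0.3, 0.4 or 0.5 SD of the paired difference, with n = 30 and a two-sided 0.05 level. The documents give no drift figure.

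Two stronger readings are not supported. One is that the study can say nothing about heels: T1-T0 still estimates the immediate effect, although no T0 test is named for it. The other is that a significant T1 versus T2 result would be false: it would be a real change over 2 hours upright in heels, with its cause unresolved.

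**What to change.** 1. In the aim and under Statistic analysis, state that T2-T1 and T2-T0 describe change over at least 2 hours of standing or walking in heels, and will not be reported as caused by heel wear alone. This costs nothing in conduct and is needed whether or not item 2 is adopted.

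2. Add one barefoot scan (T3) straight after T2 on the same device. Report T3-T0 and (T2-T3)-(T1-T0) with confidence intervals, as a descriptive partial check and not as the test of attribution. State in the plan that:
   - T3-T0 is time on the feet plus any carry-over from heels (d + r);
   - the second contrast is c - r, pulled toward zero when the heel effect persists after the shoes come off;
   - that contrast has about 1.4 times the SD of T2-T1 if reading errors are independent and equal;
   - a null result on it is inconclusive.

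The cost is one extra scan per woman and a more modest conclusion. The protocol describes the device as non-invasive and free of charge to the study, but does not state scan time or staffing, so the sponsor should confirm those. If the sponsor wants to keep the causal wording, the comparison needed is an equal period without heels, at the price of a second session of at least 2 hours.

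### The primary aim is a within-woman change from barefoot and from shoes just put on, but the plan commits to no estimate, SD or confidence interval of that change and names no paired T2 vs T0 comparison

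*Combined protocol and SAP*

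**What the plan says.** The aim, at the end of the Introduction, is to find out whether a period in heels "modifies the spinopelvic parameters compared to the barefoot condition and as soon as the shoes are worn". That is two contrasts within each woman: T2 against T0 and T2 against T1. The section The protocol measures every woman at all three times, and Parameters detected lists six parameters.

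Under Sample size, about 30 women are to be recruited as a pilot. The reason given is "Not having found similar studies in the literature", and of the number itself the plan says: "This number represents a good compromise between the possibility of finding a normal distribution and the feasibility of the study".

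Statistic analysis gives the planned output:
- A descriptive analysis of the population, to "determine the mean values and standard deviations (SD) of both the combined group and the subgroups A and S". It does not say which variables or which time points.
- A within-woman test for one contrast: if the data are normal, "for the comparison between T1 vs T2 the t-test for paired data will be used"; otherwise a Wilcoxon test of the same contrast.
- Unpaired comparisons of subgroups S and A, at T1 and at T2.
- ANOVA or Friedman on pre and post in both groups, without saying which time points these are.
- Tests "with statistical significance accepted for p values <0.05".

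The plan mentions no mean change, SD of change, confidence interval, within-woman correlation or relevant difference.

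**The concern.** The quantity that the aim asks about is never listed as a result. A reader following the plan would get group summaries and a significance verdict for T2 vs T1, with no statement of how large the change was or how precisely it was estimated. For T2 vs barefoot, half of the primary aim, not even a named paired test is planned.

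Two things are at stake. First, with about 30 women, a result of p≥0.05 is compatible with changes that may matter, and without an interval nobody can see which changes have been excluded. Second, anyone planning a later paired study would need the SD of the within-woman change, and SDs of levels do not determine it.

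**Working it through.** **The plan's own figure.** N = 30 cannot be reproduced. The document gives no effect size, SD, power, correlation or precision target. So I work out what 30 complete pairs can deliver. Two-sided α = 0.05 is assumed, because sidedness is not stated.

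**1. Precision of a mean change.** The 95% half-width is t(0.975; 29) × SD_change/√30 = 2.045/5.477 = 0.37 SD_change.

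**2. Detectable change.** From the noncentral t distribution with 29 df, the change detectable is 0.53 SD_change at 80% power and 0.61 at 90%. A true change of 0.4 SD_change has power 0.563, so it is missed about 44% of the time (1 − 0.563).

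**3. What a non-significant result leaves open.** Take t = 1.0, so p = 0.33. The estimate is 1/√30 = 0.18 SD_change and the 95% CI is 0.18 ± 0.37, or −0.19 to +0.56 SD_change before rounding the inputs. That interval contains the 0.53 SD change that the study had 80% power to find. Even with an estimate of exactly zero, changes up to 0.37 SD_change are not excluded.

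**4. From SD of levels to SD of change.** With equal SDs at both times, SD_change = SD_level × √(2(1 − r)), where r is the within-woman correlation. The document gives no r. I assume r from 0.5 to 0.95 and a target change of 0.3 SD_level at 80% power. The normal approximation is N = ((1.960 + 0.842) × √(2(1 − r))/0.3)², rounded up. The last column is the smallest N from the noncentral t.

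| r (assumed) | SD_change/SD_level | N, normal approx. | N, noncentral t |
|---|---|---|---|
| 0.5 | 1.000 | 88 | 90 |
| 0.7 | 0.775 | 53 | 55 |
| 0.8 | 0.632 | 35 | 37 |
| 0.9 | 0.447 | 18 | 20 |
| 0.95 | 0.316 | 9 | 11 |

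The same level SDs are compatible with 11 to 90 women, about eightfold (90/11 = 8.2). If r is taken as 0.8 to 0.95 only, the range is 11 to 37, about 3.4-fold.

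**5. Precision of the SD of change.** The 95% CI factors are √(29/χ²(0.975; 29)) = 0.80 and √(29/χ²(0.025; 29)) = 1.34. N varies with the square of the SD, so the upper limit alone raises a computed N by about 1.34² = 1.8 times. This is why the SD should be reported with its interval.

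**The case against.** The strongest reply is that this is a gap in planned reporting, not in the study. Every woman is measured three times, so the changes, their SDs and the correlations are all in the dataset. A paired t-test computes the mean and SD of the difference internally. If T1 and T2 means, n and an exact t are published, the SD of change follows as |mean difference| × √n / t. The descriptive means also do not depend on the normality check. If they cover each time point, the mean change is available by subtraction even when Wilcoxon is used.

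All of that stands, and it limits the point. It would be tempting to infer that the study can neither size a follow-up nor inform on a null result. The documents do not support that, because the information is collected and is partly recoverable. Recovery needs an exact t or p, which the plan does not promise. It fails from a bare p<0.05 verdict and from a Wilcoxon test, and it does not reach T2−T0, for which no paired test is named.

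Three other inferences also go too far:
- **That planning data are the pilot's declared purpose.** The word pilot only explains recruiting about 30 women without a calculation. No later study or sizing step is mentioned.
- **That no prior data exist.** The text says that no similar studies were found. The Introduction cites several studies of the immediate effect of heels and names the time factor as the gap.
- **That the study would repeat the dispute in the literature.** The Introduction does not attribute the conflicting findings to misread p-values, and the plan nowhere says that non-significance will be read as no effect.

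Finally, the descriptive SDs may be meant for participant characteristics rather than spinopelvic parameters. The text leaves this open. If so, even level SDs of the outcomes are not promised.

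**Conclusion.** The point holds as a mismatch between aim and planned output. The aim is a within-woman change on two contrasts. The plan commits to no estimate, SD or interval for either, and to a paired test for only one.

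The precision figures (±0.37 SD of the change, and 0.53 SD detectable at 80% power) assume 30 complete pairs, approximate normality and two-sided 5%. They are enough to show that p≥0.05 alone cannot support no change. The 90-to-11 range illustrates why level SDs are insufficient. It rests on an assumed correlation and an assumed 0.3 level-SD target, so it is not a forecast for this study.

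The change is well worth making because it costs almost nothing and supplies the barefoot contrast that the aim requires.

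**What to change.** Add to Statistic analysis:
- For each of the six parameters, in both the normal and the non-normal branch, the main result is the mean within-woman change T2−T0 and T2−T1 with its 95% CI. If the changes are clearly non-normal, give the Hodges-Lehmann estimate and interval.
- The SD of each change is reported with its 95% CI (chi-square if approximately normal, bootstrap otherwise).
- P-values are reported exactly and are supportive.
- The investigators set a relevant change for each parameter before looking at the data. No modification is not concluded from p≥0.05 alone; the CI is read against that figure. If the CI includes both zero and the relevant change, the result is called inconclusive.
- The variables and time points covered by the descriptive means and SDs are named.

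Cost: protocol wording, a few lines of analysis and one pre-set figure per parameter. No extra women, visits or measurements. The one real demand is that the investigators must justify the relevant changes. If they cannot do so for a parameter, its interval should be reported without a verdict of no modification.

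### Both normality thresholds are the wrong way round, and the only stated check, a graph, gives no p-value to compare with them

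*Combined protocol and SAP*

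**What the plan says.** The rule is in the second and third paragraphs of the Statistic analysis section. It begins with the check: "The distribution of the data will be verified using graphical representation". No normality test is named there or elsewhere in the document, and no criterion for reading the graph is given.

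The parametric branch follows. It opens with "If the distribution is normal ($p <0.05" and gives a paired t-test for T1 vs T2. The same branch gives independent t-tests for T1S vs T1A and T2S vs T2A, and ANOVA for the combined comparison. That sentence also sets the level for the comparisons themselves, "with statistical significance accepted for p values <0.05".

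The rank branch is: "If the data does not have a normal distribution ($p >0.05$) the Wilcoxon test will be used". It continues with Mann-Whitney for the subgroup contrasts, and then "The Friedman test will be used to simultaneously compare the pre and post of both groups".

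The Sample size section plans "recruitment of approximately 30 female subjects". The subgroup contrasts serve the secondary outcome: "The secondary outcome will be to verify in the sample analyzed whether there are different behaviors between the subgroups".

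**The concern.** In the usual normality tests a small p is evidence against normality. The plan attaches the small p to the normal branch and the large p to the non-normal branch. The two sentences agree with each other, so neither can be used to correct the other.

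The bracketed value cannot be rescued as the significance level of the outcome tests. That level is stated separately in the same sentence, and a value above 0.05 attached to non-normal data would make no sense as an outcome threshold.

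The rule decides which test is run for T1 vs T2, for both subgroup contrasts and for the combined comparison, potentially for each of the six parameters listed under Parameters detected. An analyst who adds a normality test finds that the words and the signs point to opposite tests. An analyst who uses plots has no p-value and no written criterion.

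**Working it through.** **No figure to reproduce.** The plan derives no power or sample size from this rule. The check is one of logic, followed by simulation to size the consequence.

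**Logic.**

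| Result of a standard normality test | Meaning | Branch in the plan's brackets | Branch in the plan's words |
|---|---|---|---|
| p < 0.05 | evidence against normality | t-tests, ANOVA | rank tests |
| p > 0.05 | no evidence against normality | rank tests | t-tests, ANOVA |

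**Inputs.** From the documents: n about 30; comparisons at 0.05. Assumed, because the documents give none of these: Shapiro-Wilk at 0.05; an even 15 vs 15 split; two-sided tests; normal, chi-square(10) (mildly skewed) and chi-square(4) (moderately skewed) data; effects of 0.3 and 0.5 SD (paired) and 0.8 SD (subgroups). There were 20,000 samples per cell, so the largest standard error for a power figure is √(0.5 × 0.5 / 20,000) = 0.0035.

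**Routing at n = 30.** The share with Shapiro-Wilk p < 0.05, which the brackets send to t-tests, is 4.7% for normal, 37.1% for chi-square(10) and 74.9% for chi-square(4). So 100 − 4.7 = 95.3% of normal samples go to rank tests.

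**Paired T1 vs T2, normal differences, n = 30.**

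| Effect (SD) | As written | Signs corrected | Gap (points) |
|---|---|---|---|
| 0 (type I error) | 5.0% | 5.4% | −0.4 |
| 0.3 | 34.2% | 35.9% | 1.7 |
| 0.5 | 73.4% | 75.1% | 1.7 |

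Repeat runs gave power gaps of 1.0 to 1.8 points. Part of even this gap reflects the slightly lower type I error.

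**Symptomatic vs asymptomatic, 15 vs 15.** Equal-variance t-test or exact Mann-Whitney, with the normality test applied to the 30 pooled within-group residuals.

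| Data | Type I error, as written / corrected | Power at 0.8 SD, as written / corrected | Raw gap (points) |
|---|---|---|---|
| Normal | 4.6% / 5.3% | 51.7% / 56.2% | 4.5 |
| Chi-square(10) | 3.9% / 5.1% | 54.9% / 60.1% | 5.2 |
| Chi-square(4) | 4.0% / 5.5% | 57.9% / 67.0% | 9.1 |

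The rule as written rejects less often under the null, so the raw gaps mix test size with efficiency. A further run reset each rule's cutoff to about 5% type I error. Discreteness left the as-written rule at 5.0 to 5.3%, which slightly favours it.

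| Data | Power at equal type I error, as written / corrected | Gap (points) |
|---|---|---|
| Normal | 55.4% / 56.0% | 0.6 |
| Chi-square(10) | 59.3% / 59.5% | 0.2 |
| Chi-square(4) | 60.7% / 65.5% | 4.8 |

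A smaller repeat (6,000 samples per cell, standard error up to √(0.25 / 6,000) = 0.0065) gave gaps of about 1, 2 and 4 points. The ranges are therefore about 0 to 2 points for normal or mildly skewed data and about 4 to 5 for moderately skewed data.

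**Dropping the normality check.** Plain t-tests in the same 15 vs 15 setting, at the nominal 0.05, had power of 56.0% (normal), 57.3% (chi-square(10)) and 58.5% (chi-square(4)). In that run the rule as written had 51.7%, 54.8% and 57.8%, so the gains are 4.3, 2.5 and 0.7 points. The 9-point raw gap for chi-square(4) does not carry over to this change.

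ANOVA and Friedman were not simulated.

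**The case against.** The strongest reply is that this is a drafting slip. The verbal routing is conventional: normal data to t-tests and ANOVA, non-normal data to rank tests. The one check named is a plot. Harm arises only if an analyst adds a test the plan does not mention and then follows the bracket against the words beside it. That stands, and it limits the size of the point. It does not remove the point, because the plan never says how data are assigned to a branch. Correcting the signs alone leaves no named test, and deleting the brackets alone leaves no criterion.

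It can also be said that the section's first paragraph already fixes independent t-tests for the two subgroups, without conditions. That sentence follows the means and SDs and may concern only the description of the sample. The later paragraphs make the T1 and T2 subgroup contrasts conditional on normality, so it does not settle them.

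A reader might infer that the reversed signs inflate false positives or invalidate the results. The calculations do not support this: type I error is about 5% or lower under the rule as written. A reader might also infer that the secondary comparison loses 5 to 9 points of power. Almost all of the gap for normal and mildly skewed data, and about half of it for moderately skewed data, is the lower type I error.

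**Conclusion.** The rule is wrong as written. Both thresholds are reversed, and there is no p-value for them to act on. It should be corrected before analysis because the text does not determine which test is run.

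The practical cost is conditional and small. With plots alone, the brackets do nothing. With an added test and a literal reading, most normal samples go to rank tests and many skewed samples go to t-tests. False positives do not rise. The power loss is about 1 to 2 points for T1 vs T2. For the subgroup comparison it is about 4 to 9 points raw, but only about 0 to 2 points (normal or mildly skewed) or 4 to 5 points (moderately skewed) at equal type I error. These sizes rest on the assumed test, distributions, effects and even split. The direction of the error rests on none of them.

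It would go too far to say that the plan must abandon its normality check. Prespecifying t-tests without one is a reasonable option, but the power figures do not argue for it and the error can be cured without it.

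**What to change.** Before analysis, do one of the following:

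1. Name the normality test and reverse both signs: p < 0.05 is evidence against normality and leads to the rank test; otherwise the t-test or ANOVA is used.
2. Delete both bracketed p-values and state the graphical criterion that decides the branch.

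In either case, say what is checked: the within-woman differences for the paired comparison, and within-group values or residuals for the subgroup contrasts and the ANOVA.

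If the sponsor prefers to prespecify t-tests with no normality check, more wording is needed. The text would have to define the ANOVA, say what becomes of the Friedman test, and cover the barefoot (T0) comparison in the primary aim as well as T1 vs T2.

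Options 1 and 2 each cost one or two sentences. No new data are needed, and neither the sample size nor the significance level changes.
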